1 Synopsis of the Clinical Investigation

1.1 Description of the CIP

The objectives of the Clinical Investigative Plan (CIP) are to provide a full description of the planned clinical trial. The preceding short narrative (Synopsis) introduced the goal of the project and its approach to investigate the clinical efficacy of management of early caries lesions by resin infiltration, which may be imaged through a SFE laser optical device comparable to radiographic results.

1.4 Abstract

Introduction: Research efforts using Icon have been in regard to its efficacy on treating early caries and white spot lesions. It has been found by numerous studies to be an effective form of treatment on stopping caries before traditional restorative work needs to take place. [REDACTED]

[REDACTED]

[REDACTED]

[REDACTED]

[REDACTED]

Objective: The hypothesis to be tested is that Icon performs similarly to an established prevention strategy for early caries (Oral hygiene instruction and topical fluoridation) for caries arrest; and caries progression may be imaged through a SFE laser optical device.

Materials and Methods: We propose a [REDACTED] study of Icon vs. control (Oral Hygiene Instructions [OHI]) and topical fluoridation) for early caries arrest in primary molars. Lesion depth will be performed through standard-of care methods, i.e. radiographs and visual exams, plus a novel optical device based on scanning fiber endoscope (SFE) technology for laser light imaging for early caries detection in pediatric populations. We will utilize SFE laser optical device prototypes developed by the University of Washington's Human Photonics Lab (HPL), a device already in human use for other applications, including imaging and cancer screening.

Clinical Significance: This controlled trial will assess the positive effects of [REDACTED] infiltration by ICON and may open a new therapeutic strategy in pediatric dentistry. Additionally, this study would be one of the first in vivo dental applications of the SFE optical device, and would add a novel early caries visualization technique to the armamentarium for detecting caries progression.

2 Description and Properties of the Medical Device to be investigated

2.1 Icon Kit for caries infiltration

2.2 Chemical Composition

2.2.1 Chemical Composition Infiltrant (Resin)

[REDACTED]	[REDACTED]

[figure not shown]
2.2.2 Chemical Composition Ethanol Solution (Dry-it)

[figure not shown]
[REDACTED]	[REDACTED]
[REDACTED]	[REDACTED]
[REDACTED]	[REDACTED]

[figure not shown]
2.2.3 Chemical Composition HCl Etching Gel (Hydrochloric Acid Gel)

[figure not shown]
[REDACTED]	[REDACTED]

[figure not shown]
2.3 Instructions for use

3 Objectives of the Clinical Investigation Plan (CIP)

The objectives of the CIP are to provide a full description of the planned clinical trial. The preceding short narrative (Synopsis) introduced the goal of the project and its approach to investigate the clinical effectiveness of management of caries lesions by resin infiltration.

The Background and Rationale section addresses the relevance of the project to oral health and rationale for the proposed project. The existing knowledge is briefly stated, including literature citations and highlights of relevant data, indicating the gap that the project is intended to fill.

The research plan includes the Study Design and Methods addressing the hypotheses to be tested, followed by Specific Aims. The data collection and analysis (including assessment of statistical significance) will be described and used to prove or disprove the hypotheses.

Previous experience with the material involved is described including attention to risk analysis. Expected results, potential difficulties and limitations are discussed and solutions or alternative approaches are indicated.

4 Preliminary Investigations and Justification of the CIP

4.1 Background and Rationale

Icon, by DMG, is a caries infiltration system developed to arrest early caries rather than drill, fill or “wait and see.” Icon is used as a restorative therapy for caries lesions thought of as too early for conventional restorative treatment. Icon prevents lesion progression and increases life expectancy for the tooth by establishing a diffusion barrier which prevents cariogenic acids from breaking down tooth structure and causing further demineralization. This barrier also serves to help maintain the mineral content of the dentition by blocking mineral content from leaching from the tooth. Icon is also an aesthetic treatment for white spot lesions by allowing the white spot to take on the appearance of the surrounding healthy enamel.

White spot lesions occur when the sub-surface porosity of the lesion fills with an air/fluid mixture thus changing the way light is refracted.⁴ This change in refractive index causes the tooth to appear milky, yellow or brown in color and can also diffuse in streaks across the teeth. These discolorations can also be caused by excessive exposure to fluoride during development, also known as fluorosis. White spots, or areas of demineralization, often indicate early caries lesions and there are currently a few treatments to prevent further acid damage.

Current alternative forms of treatment for early caries include the following: 1) microabrasion, 2) fluoride treatments, and 3) sealants/commercial adhesives. Microabrasion tends to be used more for cosmetic purposes, and unlike Icon, is not used to arrest caries. A study on eight orthodontic patients with white spot lesions found that using microabrasion improved the cosmetic appearance of these lesions.²³ However, the authors suggest that this treatment is far from standard-of-care and there should be further research into the effects of microabrasion on loss of enamel and tooth structure.

Studies involving the topical application of fluoride to early caries lesions have demonstrated high rates of caries prevention, arrest, and/or reversal effectiveness, in both children and adults.¹⁴ Although full mineral recovery might be achieved through such measures, in the case of shallow enamel lesions, the same treatment in deeper white spot lesions have demonstrated negligible remineralization effects.³⁶ Furthermore, the esthetic effect on white spots is often not corrected with the application of fluoride treatments; and thus, defeating one of the main purposes of treating white spots or areas of demineralization.

The use of sealants or commercial adhesives to halt the progression of early caries has also been researched. However, these studies have shown that these materials are unable to fully penetrate the lesion, leaving potential for further demineralization.²² To prevent progression, it was necessary to treat the area deeper than just the immediate surface area, which these products are unable to do.

Icon is unique in that it can penetrate deeper into the tooth to arrest caries progression. Also, unlike the other treatment options discussed previously, it works on both halting caries progression as well as diminishing white spots/demineralization area appearance for better esthetics results.

In vitro and in vivo studies have been done on the treatment of caries lesions with resins such as Icon. A number of studies were found in which Icon by DMG was used to evaluate the effect on these lesions. Each of the studies reviewed verified that Icon can be used as a restorative treatment for early caries and white spots.²⁵ Another study evaluated Icon's application time on penetration of enamel caries. This study found that three minutes was a sufficient time for the Icon to penetrate caries lesions.²⁰

From an aesthetic standpoint, Icon was found to be an effective treatment in masking white spot lesions.³¹ This in vitro study monitored the effect of Icon on white spots over an eight week period. Icon had a significant effect on returning the subjected teeth to their natural color, whereas the fluoride toothpaste and gel applications did not.

Current standard-of-care for early caries detection relies on visual examinations with tactile sensation, aided by radiographs. Typically an explorer is used to determine enamel surface hardness, and visual clues such as color and translucency are relied upon to evaluate the caries status of a patient. The methodology is unsophisticated and fails to differentiate between varies stages of caries progression. In a study of 12 year old children with caries, it was found that the visual/tactile method, with or without diagnostic adjuncts, can diagnose cavitated lesions efficiently, but not non-cavitated carious lesions.³ Furthermore, visual-tactile techniques are known to be unreliable due to subjectivity. Lesions can go undetected because teeth are typically examined by the naked eye, and there is need for supplemental analysis when faced with clinical signs that will leave a dentist uncertain, including dark occlusal or approximal shadows.¹⁵ Caries detection through radiograph examination is problematic because it is a flawed imaging system; and caries is detected after it has progressed through enamel and/or dentin.^{9,17}

The last 2 decades have seen various technological advances developed toward visualization and evaluation of caries. These include quantitative laser or light fluorescence (QLF), electrical conductance measurements (ECM), infrared (IR) laser fluorescence, direct digital radiography and Digital Imaging Fiber-Optics Trans-Illumination (DIFOTI). The research and data supporting effectiveness of this technology are at different stages of development, but there is no gold standard for dental imaging devices thus far.²³

The scanning fiber endoscope was developed at the University of Washington's Human Photonic Laboratory (HPL) over the past decade. A completely new imaging technology was developed to provide high-resolution imaging from a very small and flexible scope. By placing a sub-millimeter fiber-optic scanner and lens assembly at the scope tip, the number of pixels (picture elements) is no longer related to the number of camera sensor elements. The result is near HDTV resolution from a scope the size and feel of a single strand of cooked spaghetti, with production of real time color video-rate images with 600 X 600 line resolution using scanned low-power red, green, and blue laser light.

The ultrathin endoscope developed at the UW Mechanical Engineering Department has been applied to numerous biomedical areas such as esophageal cancer screening, bile duct imaging, and bladder surveillance. This threadlike imaging device is less than 1.5 mm in diameter and is highly flexible behind its short rigid tip, making it ideal for intraoral use in pediatric populations. (See Figure 1.)

[figure not shown]

Figure 1: The ultrathin Scanning Fiber Endoscope (SFE) optical device is pointed toward the occlusal surface of an extracted human molar. The threadlike imaging device is less than 1.5 mm in diameter.

Following the trend for higher performance in low-cost lasers used in DVD players, a violet laser light source has been integrated into the system for detecting early stages of tooth decay. Enhanced surface detail of teeth is more apparent using violet 405-nm wavelength compared to red 635-nm wavelength illumination, as shown in monochrome images of the same tooth (See Figure 2).

[figure not shown]

Figure 2: Monochrome images of the same tooth taken with red (635nm) and violet (405nm) laser light using the device in Figure 1.

The majority of visible light from conventional incandescent and natural light sources consists of wavelengths closer to the red 635-nm that penetrates more deeply into the tooth. Compared to images obtained at 635-nm, images captured using a violet light are not contaminated and blurred by superposition of light reflected from dental tissue at greater depths. Thus, 405-nm laser illumination of enamel surfaces of teeth produces enhanced image details. The ultrathin endoscope with short-wavelength illumination may be used to visualize surface manifestations of phenomena such as demineralization associated with early caries, thus better aiding the clinician for detection of tooth decay before caries progresses into cavitation.

Currently no single method for caries detection can be used on all tooth surfaces under all conditions. These diagnostic devices and methods lack sensitivity and specificity; with caries detection at a point when surgical or restorative intervention is required. Additionally, these optical imaging devices are cumbersome, and often lead to inaccuracy due to user failure. Ultimately, these approaches result in caries lesions diagnoses overlooked at the earliest stages when less invasive measures, including remineralization techniques such as Icon, may be effective. Clinical caries detection sensitive to early lesions would bring about innovations in treatment modalities through medicinal therapeutic and preventive approaches, including chemotherapeutic approaches such as Icon. An imaging system such as the SFE optical device, specifically designed for dentistry, would be the ideal approach.

4.2 Hypotheses

4.2.1 Hypothesis I

The hypothesis to be tested is that Icon performs similarly to an established prevention strategy for early caries (Oral hygiene instruction and topical fluoridation) for caries arrest.

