4.3.4 Clinical Studies

Infiltrating a caries lesion is a currently introduced strategy to strengthen damaged tooth structure and to reduce caries progression without any surgical intervention.³⁹⁻⁴⁰ Management of early lesions by infiltrating instead of or postponing restorative treatment would have a great impact towards improving oral health care by means of its non-invasive nature. It will drastically lengthen the life-cycle of a tooth.²⁵ Infiltration would provide a simple and cost-effective management option with the least possible iatrogenic effect and diminished need for future re-treatment due to deteriorating of restoration margins.⁴¹

The promising in vitro results of caries infiltration on extracted teeth were underlined by different clinical trials. Several groups reported slower caries progression in infiltrated sites compared to controls: Radiographically obtained quantification reveals lesion progression in 16% of infiltrated sites compared to 53% for controls after one year and for 24% (infiltration group) and 62% (control) after two years. Recently, the three year follow-up data were published, reporting 32% progression for infiltrated lesion and 70% for controls in this split-mouth study.⁴² Meyer-Lueckel et al. measured progression rates of 7% (infiltrated sites) and 37% (controls) after 18 month in young adults.⁴³ The currently available 3-year data of this study report 4% progression in infiltrated lesion and 42% for controls.⁴⁴ Ekstrand et al. aimed to assess the efficacy of resin-infiltrated lesions covered by fluoride varnish (FV) versus FV treatment only of proximal lesions on deciduous molar teeth in a one year split-mouth study. Radiographically, 23% of the test lesions and 62% of the control lesions had progressed, comparable to the aforementioned results in young adults.⁴⁵

5 Device Risk Analysis and Assessment

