9.3 Randomization

25 non-cavitated early caries lesions will be randomly assigned, using a random numbers table, to study arm 1) the Icon treatment group; and 25 non-cavitated early caries lesions will be randomly assigned, using a random numbers table, to study arm 2) the Control group (OHI and topical fluoridation).

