11.4 Statistical Analysis

11.4.1 Descriptive Statistics

Descriptive statistics (means, standard deviations, counts, and percentages) will be calculated for all variables. A Chi-square test of association will be performed to evaluate if there is a significant difference in caries arrest by treatment group at a significance level of 0.05. Additional Chi-square tests of association will be performed to determine if there is a significant association with the secondary outcomes by treatment group.

11.4.2 **Blinding**

Each subject enrolled into this study will be assigned a unique identifying code number. Every effort will be made to maintain the confidentiality of each study subject's identity. No presentation or publication of the study data will identify any study subject.

11.4.3 **Evaluation of Records**

SFE laser optical device image diagnoses from each time point will be compared to diagnoses from radiograph and visual exams from chart review from the same visit.

- For radiograph and visual exams: Assessments of caries lesions per standard of care will be abstracted from the electronic dental record system (Axium) and recorded on CRF.
- For SFE laser optical device image: Recordings from the device will be used to assess caries lesions and recorded on CRF.

11.4.4 **Missing Data**

Missing data due to dropouts have been accounted for in adjusted sample size. The missing data will be at random. Data of dropouts will be assigned as "last observation carried forward".

11.4.5 **Statistical Software**

STATA Data Analysis and Statistical Software will be utilized to perform data analysis.

12 Method of Reporting

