The primary endpoint in this study is the proportion of study lesions that have progressed, whereby a difference in caries progression of 40% after 2 years between resin infiltrated teeth and control will be assumed. This difference is based on a previous infiltration study by Ekstrand et al. [45] who reported a 1-year difference in caries progression in primary teeth of 39% (resin infiltration (23%) vs. control (62%)), which was furthermore comparable to results obtained in young adults. Martignon et al [42] for example reported a difference in caries progression in permanent teeth of 37% and 38% after 1 and 2 years respectively; and Meyer-Lueckel et al. of 30% after 18 months.

Based on an assumed difference in caries progression of 40% between resin infiltrated teeth and control, with alfa = 0.05 and a power of 80% the calculated sample size (t-test; matched pairs) would be 42 lesions to find significant differences. To allow for a potentially attrition rate of at least 20% over a period of 2 years a total of 50 lesions will be included.

Statistical Analysis

All evaluations are performed by one trained examiner. The primary outcome is proportion of study lesions that progressed after 2 years as measured via dental examination and pairwise comparison of radiographs. Differences between groups will be tested using Fisher's exact test.

Secondary outcomes are the proportion of study lesions that progressed after 1 year as well as change in categorical lesion depth (progression to next depth category lesion; E1->E2->D1->D2->filling) after 1 and 2 years as measured by pairwise comparison of radiographs. In addition, the change in categorical lesion depth will be determined via SFE laser optical device imaging after 1 and 2 years and compared to the change in categorical lesion depth as measured by pairwise comparison of radiographs. Differences in categorical lesion depth will be analyzed with Chi-square tests with 95% confidence interval (95% CI) and P = .05.

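### Hypothesis I states similar performance of Icon and control, but the trial is sized and tested only for a difference, so a non-significant result would not show similarity

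*Combined protocol and SAP*

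**What the plan says.** **Stated hypothesis.** Protocol section 4.2.1: "The hypothesis to be tested is that Icon performs similarly to an established prevention strategy for early caries". The Objective paragraph of the abstract (section 1.4) uses the same wording. Section 3 says that data collection and analysis, including statistical significance, "will be described and used to prove or disprove the hypotheses".

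**Working statistics.** SAP, Sample Size Determination, on the primary endpoint of lesions that progressed: "whereby a difference in caries progression of 40% after 2 years between resin infiltrated teeth and control will be assumed". With alpha 0.05 and 80% power this gives 42 lesions, raised to 50 for attrition. The SAP's Statistical Analysis section tests the groups for a difference with Fisher's exact test. Protocol section 11.4.1 plans a Chi-square test "to evaluate if there is a significant difference in caries arrest by treatment group at a significance level of 0.05". Section 9.3 allocates 25 lesions to each arm.

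**Expected direction.** The Clinical Significance paragraph of the same abstract says "This controlled trial will assess the positive effects of" infiltration. Section 4.3.4 summarises earlier trials: "Several groups reported slower caries progression in infiltrated sites compared to controls".

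**Not found.** The visible text has no equivalence or non-inferiority margin, no interval-based rule for the primary outcome, and no statement of how a non-significant primary test is to be interpreted. Parts of the abstract are blacked out.

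**The concern.** The hypothesis and the test point in opposite directions. If similarity is what the trial should show, a test of no difference cannot show it: failing to reject may only mean that the sample was too small. If the aim is to show a benefit, which the sizing and background suggest, Hypothesis I states the opposite of what the investigators expect.

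What is at stake is the reading of a non-significant result. A report that follows Hypothesis I and section 3 literally could present such a result as confirming similar performance. In a trial of 50 lesions, that result is compatible with a large true benefit and also with real harm.

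**Working it through.** **Inputs.** 25 lesions per arm (protocol section 9.3). Alpha 0.05 (SAP; taken as two-sided). Source rates 23% with infiltration and 62% with control (SAP, from a 1-year trial in primary teeth). All other event rates and all margins are assumptions. Lesions are treated as independent and all analysed unless stated.

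**1. The plan's own figure is a size for detecting a difference.** Take 23% and 63% (the 23% source rate plus the assumed 40 points), unpooled normal approximation, two-sided 0.05, 80% power:

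n per arm = [p1(1-p1) + p2(1-p2)] × (1.96 + 0.8416)² / d² = (0.1771 + 0.2331) × 7.849 / 0.16 = 20.1, so 21 per arm and 42 in total.

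This matches the SAP's 42. The SAP names a matched-pairs t-test and does not give every input, so its exact route is not certain. The other route tried that gives 42, a one-sided two-sample t-test with standardised effect 0.8, is also a calculation for a difference.

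**2. How often the planned test is non-significant when a real difference exists.** Sum the binomial probabilities of all tables with two-sided Fisher p > 0.05:

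| True rates, Icon vs control | Difference | 25 per arm | 20 per arm |
|---|---|---|---|
| 42% vs 62% | 20 points better | 76% | 86% |
| 32% vs 62% | 30 points better | 49% | 66% |
| 27% vs 62% | 35 points better | 35% | 52% |
| 23% vs 62% (source rates) | 39 points better | 24% | 40% |
| 82% vs 62% | 20 points worse | 76% | 80% |

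The 20-per-arm column is the case in which 20% of lesions are lost and not carried forward. At 25 per arm, the true benefit at which non-significance is a coin toss is 28.0, 29.7, 29.8 and 29.8 points for control rates of 40%, 50%, 60% and 70%.

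**3. What identical results would show.** For 10/25 in each arm the Wilson 95% limits are 23.4% and 59.3%. The Newcombe interval for the difference is ±√[(0.400 - 0.234)² + (0.593 - 0.400)²] = ±0.254, that is -25 to +25 points.

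**4. What a similarity claim would need (illustrative margin of 20 points).**

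- *Two-sided equivalence at 25 per arm.* The chance that the 95% Newcombe interval lies within ±20 points is 1% when both true rates are 23%, and essentially zero at 40%, 50% or 62%.
- *Equivalence size, 80% power.* n per arm = 2p(1-p)(1.96 + 1.2816)² / 0.20². At 23%, 50% and 62% this gives 94, 132 and 124. With one-sided 0.05 on each side (1.645 in place of 1.96) it gives 76, 108 and 101.
- *One-sided non-inferiority size, equal true rates, 80% power.* n per arm = 2p(1-p)(1.96 + 0.8416)² / 0.20² = 70, 99 and 93 at the same rates.
- *One-sided non-inferiority power at 25 per arm* (upper 95% Newcombe limit below the margin):

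| True rates, Icon vs control | Margin 10 | Margin 15 | Margin 20 |
|---|---|---|---|
| 23% vs 62% | 95% | 99% | 99% |
| 32% vs 62% | 82% | 93% | 96% |
| Equal, 23% to 62% | 10–14% | 23–25% | 34–42% |

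Non-inferiority is therefore feasible at the planned size if the expected benefit is real, but not if the arms truly perform alike.

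**5. Fisher and the interval can disagree.** For 8/25 vs 15/25, Fisher p = 0.088, while the Newcombe 95% interval is -50.2 to -0.5 points and excludes zero. If both are reported, the plan must say which one decides.

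**The case against.** The strongest reply is that Hypothesis I is a loosely worded null. On that reading the documents agree: no difference is the null, Fisher or Chi-square tests it at 0.05, and power is set against a 40-point alternative. Section 6.1 gives the main purpose as evaluating the resin's efficacy, and a statistician following the SAP would run an ordinary difference test. Section 3 is a general outline of the plan that covers both hypotheses and is not a decision rule. No passage says that a non-significant result will be reported as similarity. The non-significance rates are ordinary limited power for effects below 40 points and would be the same however the hypothesis were worded.

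Much of this stands. The primary test is usable, the 42 is not in dispute here, and misreporting is a risk the plan leaves open, not one it prescribes. The margin-based figures are illustrative only. But nothing labels Hypothesis I a null, and even as a null it cannot be proved by a non-significant test, which the wording of section 3 would allow. Limited power is exactly why the reading of a non-significant result needs to be fixed in advance.

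Two limits also stand. Up to two lesions per child may be enrolled (section 6.4), so independence is an assumption. And the absence of a margin can be asserted only for the visible text.

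**Conclusion.** The concern holds. Hypothesis I and the abstract state a similarity claim that neither the sample size nor the planned tests can establish, and the interpretation of a non-significant result is left open. At 25 lesions per arm, non-significance is more likely than not whenever the true benefit is below about 28 to 30 points (control progression 40% to 70%), and a 20-point harm would be missed about as often as a 20-point benefit, 76% of the time. These figures rest on two-sided 0.05, independent lesions and complete data. With 20 lesions per arm, non-significance at the source rates rises from 24% to 40%.

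This should be corrected, but it does not invalidate the primary test as a test of a difference. Confidence is high on the mismatch. Whether a report would actually claim similarity cannot be known from the plan.

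**What to change.** - **Protocol section 4.2.1 and abstract.** Restate Hypothesis I as a difference: *the proportion of study lesions that have progressed by 2 years differs between Icon and control, and is expected to be lower with Icon; the null is no difference.*
- **SAP, Statistical Analysis.** Report the risk difference with a 95% confidence interval beside the Fisher p-value, name the interval method, and state that the Fisher p-value decides significance.
- **SAP, interpretation.** State that a non-significant result is inconclusive and is not evidence of similar performance.
- **If the sponsor keeps a similarity claim.** Prespecify and justify a margin, say whether the claim is one-sided non-inferiority or two-sided equivalence, use an interval-based test, and revisit the sample size.

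The first three changes take a few sentences and leave the sample, visits and data collection as they are. What is given up is a similarity claim that the present design could not support. Keeping such a claim could be far more costly: at an illustrative 20-point margin, non-inferiority with equal true rates or two-sided equivalence would need about 70 to 132 lesions per arm in place of 25. Non-inferiority fits the planned sample only if the expected benefit is real.
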